1 REVISION HISTORY

| Revision | Date Issued | ECO Number |
|----------|------------------|------------|
| A | December 4, 2018 | 2605 |

2 PROTOCOL SYNOPSIS

| | |
|------------------------------------------|--------------------------------------------------------------------------------------------------------------------------------------------------------------------------------------------------------------------------------------------------------------------------------------------------------------------------------------------------------------------------------------------------------------------------------------------------------------------------------------------------------------------------------------------------------------------------------------------------------------------------------|
| Protocol Title | Pilot Study of the TearCare™ System – Long-Term Extension |
| Protocol ID Number | 06215 |
| Study Device | TearCare™ System |
| Intended Use | The TearCare™ System is indicated for the application of localized heat when the current medical community recommends the application of a warm compress to the eyelids of adult patients. Such applications would include Meibomian Gland Dysfunction (MGD), Dry Eye, or Blepharitis. |
| Primary Objective | Evaluate the long-term clinical utility, safety, and effectiveness of re-treatment with the TearCare™ System in adult patients with dry eye syndrome. |
| Study Design | Single center, prospective, non-randomized case series |
| Primary Effectiveness Endpoint | Tear Breakup Time at 4 weeks |
| Secondary Effectiveness Endpoints | 
 • Meibomian Gland (MG) Assessment: 
 ○ # Glands yielding clear liquid secretions ○ # Glands secreting any liquid ○ Total MG Score • Dry Eye Symptoms and Quality of Life as measured by: 
 ○ Standard Patient Evaluation of Eye Dryness (SPEED) Questionnaire ○ Ocular Surface Disease Index (OSDI) Questionnaire ○ Symptom Assessment in Dry Eye (SANDE) Questionnaire • Corneal & conjunctival staining scores |
| Safety Endpoints | 
 • Device-related adverse events • Best spectacle-corrected Snellen visual acuity |

| | |
|---------------------------|----------------------------------------------------------------------------------------------------------------------------------------------------------------------------------------------------------------------------------------------------------------------------------------------------------------------------------------------------------------------------------------------------------------------------------------------------------------------------------------------------------|
| Inclusion Criteria | 
1. Previously enrolled in the TearCare arm of the TearCare Pilot Study (protocol number 05429)2. Reports dry eye symptoms within 3 months of the baseline examination with a Standard Patient Evaluation for Dryness (SPEED) score ≥ 63. TBUT of <10 seconds in at least one eye4. Willing to comply with the study, procedures, and follow-up5. Willing and able to provide consent |
|---------------------------|----------------------------------------------------------------------------------------------------------------------------------------------------------------------------------------------------------------------------------------------------------------------------------------------------------------------------------------------------------------------------------------------------------------------------------------------------------------------------------------------------------|

| Exclusion Criteria | 1. Any active ocular or peri-ocular infection or inflammation 2. Recurrent eye inflammation [REDACTED] 3. Ocular surgery, oculoplastic surgery, ocular injury, Ocular Herpes Simplex, or Herpes Zoster 4. Ocular surface abnormalities that may affect tear film distribution or treatment 5. Abnormal eyelid function in either eye 6. Diminished or abnormal facial, periocular, ocular or corneal sensation 7. Ocular surface abnormalities such as corneal epithelial defects, ulcers, corneal dystrophies 8. Systemic diseases resulting in dry eye (e.g. Sjogren's syndrome) 9. Allergies to silicone tissue adhesives 10. An absence or fibrosis of the Meibomian glands (e.g. ectodermal dysplasia) 11. Unwillingness to abstain for the duration of the study from systemic medication known to cause ocular dryness (e.g. Accutane, antihistamines, etc.) 12. Anyone who requires chronic use (i.e. for any portion of the study) of topical ophthalmic antibiotics, steroids, non-steroidal anti-inflammatory medications or who has been on any of these medications [REDACTED] [REDACTED] 13. Participation in another ophthalmic clinical trial [REDACTED] [REDACTED] 14. Co-existing conditions that could interfere with the assessment of safety or efficacy of treatment (e.g. macular disease, pregnancy, nursing, etc.) |
|--------------------|------------------------------------------------------------------------------------------------------------------------------------------------------------------------------------------------------------------------------------------------------------------------------------------------------------------------------------------------------------------------------------------------------------------------------------------------------------------------------------------------------------------------------------------------------------------------------------------------------------------------------------------------------------------------------------------------------------------------------------------------------------------------------------------------------------------------------------------------------------------------------------------------------------------------------------------------------------------------------------------------------------------------------------------------------------------------------------------------------------------------------------------------------------------------------------------------------------------------------------------------------------------------------------------------------------------------------------------------------------------------------------------|
|--------------------|------------------------------------------------------------------------------------------------------------------------------------------------------------------------------------------------------------------------------------------------------------------------------------------------------------------------------------------------------------------------------------------------------------------------------------------------------------------------------------------------------------------------------------------------------------------------------------------------------------------------------------------------------------------------------------------------------------------------------------------------------------------------------------------------------------------------------------------------------------------------------------------------------------------------------------------------------------------------------------------------------------------------------------------------------------------------------------------------------------------------------------------------------------------------------------------------------------------------------------------------------------------------------------------------------------------------------------------------------------------------------------------|

Pilot Study of the TearCare™ System – Long-Term Extension
06215 - Rev A

| | |
|----------------------------------------|------------------------------------------------|
| Study Duration for Each Subject | 6 months |
| Proposed Duration of Study | 8 months |
| Schedule of Visits | Baseline/Treatment, 1 month, 3 month, 6 months |
| Number of Centers | 1 |
| Number of Subjects | 12 |

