11 STUDY PROCEDURES

11.2 NUMBER OF SUBJECTS AND STUDY DURATION

Up to 12 subjects will be enrolled in the study. Each subject will receive one in-office TearCare procedure and then will be followed for 6 months. It is anticipated that enrollment in the study will take 1-2 months. Including the 6-month follow-up period, the study is expected to last 7-8 months.

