11.5.4 MANAGEMENT OF DRY EYE SYMPTOMS DURING FOLLOW-UP

During follow-up, if subjects require relief of their dry eye symptoms, they should only use the same type of drops or lubricants they used prior to the start of the study. Subjects should record their daily use of lubricants on the Lubricant Drop log.

Subjects **should not** use any other method of relieving dry eye symptoms, including any of the following:

- Warm compress
- Restasis or Xiidra
- Other dry eye treatments (e.g. Lipiflow, TrueTear, iLux, punctal plugs, etc.)

NOTE: If a subject had a punctal plug at the baseline visit and it falls out during the study, it should be replaced.

Review these instructions with subjects at the end of the Baseline visit and provide them with the Lubricant Drop log. They should complete the log each day and bring it back to the clinic at each follow-up visit.

[figure not shown]

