13.4 RISKS ASSOCIATED WITH PARTICIPATION IN THE CLINICAL INVESTIGATION

As with any type of eye procedure, there are potential risks that are associated participating in the investigation including:

- Post-procedure Discomfort
- Blurred Vision
- Inflammation of eyelids

In addition, subjects who are asked to discontinue pre-procedure dry eye medications may note that their eyes feel drier. All anticipated study risks are listed in Section 12.2.

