13.6 STEPS THAT WILL BE TAKEN TO CONTROL OR MITIGATE THE RISKS

The major risks to the subjects and the steps taken to control or mitigate them are described below:

1. Overheating of the eyelids: All TearCare treatments will be done in the investigator's office under direct supervision of the investigator. The device delivers heat to the eyelids at a temperature ranging from 41-45°C. This temperature range was selected because it is both safe for eyelid heating and effective for melting obstructions in the meibomian glands.^{33,34,35,36} The user can adjust the temperature up or down to a level that is comfortable and may also

shut off the System at any time if it is too uncomfortable or painful. In addition, the TearCare System continuously monitors and regulates the temperature at the tissue-contacting surface of the iLid devices and has been designed to not exceed the maximum allowable temperature.

2. Corneal abrasion: If the iLid devices are not positioned properly or come loose during the treatment, there is the potential for a corneal abrasion. To mitigate this, the supervising physician will apply the strips to the subject and will monitor their position during the treatment to ensure they remain in place and secure.

In addition, there is the possibility of corneal abrasion or abrasion of the eyelid surface during expression of the meibomian glands. To reduce the chance of abrasion, the forceps have been designed with smooth surfaces (i.e. no rough edges) and only trained users will perform expression.

3. Worsening of dry eye symptoms: It is possible that subjects will experience a worsening of dry eye symptoms during the study. Subjects will undergo a complete eye exam at each visit and if any untoward or worsening signs of ocular surface disease are observed, they will be treated appropriately.

In addition to the above, the following mitigation steps have also been taken to reduce the risks in this study:

- The device has been tested to demonstrate that it meets performance and safety specifications, as described in Section 7.1.
- Instructions for Use are provided with each device.
- The ophthalmologist using the device is board-certified and has experience in how safely and correctly apply and remove the iLid devices, and operate the TearCare System.

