13.7 RISK-TO-BENEFIT RATIONALE

The risks in this study are low, due to the non-invasive nature of the TearCare System. In addition, these risks are generally temporary and are readily treatable or reversible with no medical intervention or, in some cases, using standard medical treatment.

Against these low risks are the potential for a reduction in subjects' eye discomfort and symptoms due to dry eye syndrome. Reduction in dry eye symptoms holds the possibility of several related benefits to the subjects, including:

- Improved vision
- Improved productivity
- Reduced dependence on medications and lubricants while simultaneously improving physiologic tear production ("your own tears")

- Reduced costs to subjects to treat their dry eye symptoms

On the basis of this analysis, the potential benefits to subjects related to treatment with the TearCare System outweighs the relatively low risk associated with the System.

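### No solicited safety assessment is visible between treatment and the 1-month visit, so mild early events may be under-reported and a transient acuity change may be missed

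*Combined protocol and SAP*

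**What the plan says.** The Schedule of Visits in the synopsis (Section 2) reads "Baseline/Treatment, 1 month, 3 month, 6 months". Section 11.2 adds: "Each subject will receive one in-office TearCare procedure and then will be followed for 6 months". The period just after the procedure therefore falls wholly between the first two listed visits.

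Section 13.4 lists "Post-procedure Discomfort", "Blurred Vision" and "Inflammation of eyelids" as risks of taking part. Section 13.6 adds overheating of the lids and says of a misplaced or loose device that "there is the potential for a corneal abrasion". It also names abrasion during gland expression, and worsening of dry eye symptoms at any time in the study. Section 13.7 sums up that "these risks are generally temporary and are readily treatable or reversible with no medical intervention", or in some cases with standard treatment. It gives no duration in days or weeks.

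The safety endpoints visible in Section 8.2 are device-related adverse events and best spectacle-corrected Snellen acuity. Section 12 requires ocular adverse events during the trial to be documented whether or not they are device related. Sections 12 and 12.3 require the date, severity, treatment and relationship to be recorded. Section 13.6 ties the full eye examination to visits.

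Two contacts between visits are visible. Section 11.5.4 gives subjects a daily Lubricant Drop log: "They should complete the log each day and bring it back to the clinic at each follow-up visit". Section 11.6 provides a reminder call a few days before each follow-up visit, about not using drops beforehand. Neither is described as asking about harms.

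**The concern.** The protocol names several harms that would arise at or soon after a single procedure and regards them as mostly temporary. The first listed visit after that procedure is about four weeks later. A duty to document an event is not a means of finding it. A subject with a few days of sore lids or blur may not telephone, and may not mention or date it accurately a month on. Acuity is more exposed still, because it exists only where it is measured. If vision dipped and recovered before the visit, the 1-month value cannot show it.

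Safety is part of the study objective (Section 4). The pilot reported no adverse events in either group (Section 7.2), so a low count here would be read as corroboration. Incomplete capture makes a low count more likely whatever the true rate. The study is unmasked (Section 9), and identifying adverse events rests with the principal investigator (Section 12.3), who is a co-inventor of the device (Section 6.4). Dated entries made by the subject at the time would lessen the reliance on memory and on one person's questioning.

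**Working it through.** **The plan's own figure.** The sample size of 12 is the headcount of the pilot's TearCare arm (Section 14.2). There is no power calculation to reproduce, and the point does not depend on one. The documents give neither incidence nor duration for any named harm, so the calculations below are illustrations under stated assumptions.

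**Step 1. What is looked at, and when.**

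| Item | Where | Covers the first days after treatment? |
|---|---|---|
| Listed visits | Synopsis | No; next visit is at 1 month |
| Full eye examination | 13.6 | At visits only |
| Lubricant Drop log | 11.5.4 | Daily, but described as recording lubricant use only |
| Reminder call | 11.6 | A few days before the visit, about lubricants |
| Adverse-event documentation | 12, 12.3 | Yes as a duty, with date of event; no way of eliciting events is visible |

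**Step 2. Effect of incomplete capture on the adverse-event count.** Let p be the assumed share of subjects with a mild early event and c the assumed share of those events captured by report or recall. Expected recorded events = 12 × p × c. Chance of recording none = (1 − p × c)^12.

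At p = 25%:

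- c = 100%: 12 × 0.25 = 3.0 expected; 0.75^12 = 0.032.
- c = 70%: 12 × 0.175 = 2.1 expected; 0.825^12 = 0.099.
- c = 30%: 12 × 0.075 = 0.9 expected; 0.925^12 = 0.392.

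The same formula over a range of p gives the chance of recording none:

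| p | c = 100% | c = 70% | c = 30% |
|---|---|---|---|
| 10% | 0.28 | 0.42 | 0.69 |
| 20% | 0.07 | 0.16 | 0.48 |
| 25% | 0.03 | 0.10 | 0.39 |
| 30% | 0.01 | 0.06 | 0.32 |

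**Step 3. What an examination at day 28 would still see.** This applies to acuity and slit-lamp findings, not to reported or recalled events. Assume exponentially distributed durations with mean m days and onset at treatment. The share still present at day 28 is s = exp(−28/m): about 0 for m = 2, 0.018 for m = 7, 0.135 for m = 14 and 0.368 for m = 28. The chance that at least one of 12 subjects still shows the finding is 1 − (1 − p × s)^12.

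| p | Ever occurs in ≥1 subject | m = 2 | m = 7 | m = 14 | m = 28 |
|---|---|---|---|---|---|
| 10% | 0.72 | about 0 | 0.02 | 0.15 | 0.36 |
| 20% | 0.93 | about 0 | 0.04 | 0.28 | 0.60 |
| 30% | 0.99 | about 0 | 0.06 | 0.39 | 0.75 |

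If the changes last days, the 1-month examination would almost never see one. If they last weeks, it often would.

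**Step 4. Limit from sample size alone.** With perfect capture, 0 events in 12 has a two-sided exact 95% upper limit of 1 − 0.025^(1/12) = 26.5%. Incomplete capture adds a downward bias to what is already an imprecise estimate.

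**The case against.** **Adverse events are collected throughout.** A reader might infer that the adverse-event endpoint is read only at 1 month, after the harms have gone. The documents do not support this. Sections 12 and 12.3 cover the whole trial and record the date of the event, so a resolved event can still be entered. What remains is possible under-reporting, not an absence of collection.

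**No duration is given.** A reader might also infer that the harms would all have resolved by 1 month. Section 13.7 says only that they are generally temporary. 'May have resolved' is as far as the text goes.

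**A nil count need not be the expected result.** It is tempting to say that few or no events would be expected whether or not harms occurred. At p = 25%, at least one event is recorded with probability 61% to 90%. A nil count is more likely than not only in one corner of the grid (10% incidence, 30% capture), and the documents cannot say whether the trial sits there.

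**Not every named harm is short-lived.** Worsening of dry eye symptoms is one of the three major risks in Section 13.6, and visits at 1, 3 and 6 months suit it. Those visits also fit the long-term aim in Section 4. The point is limited to the procedural harms. The visible adverse-event endpoint in Section 8.2 nevertheless carries no time limit, so early events belong in it.

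**Text is missing.** The bodies of 11.1 (with Table 2), 11.5.3 and 12.2 are not in the public text, and parts of 8.2 and 11.6 are redacted. A check on the treatment day can be neither confirmed nor excluded, and its absence cannot be charged to the plan. Such a check would not cover the following days, however, and a reading soon after expression under topical anesthesia (Section 6.5) might understate discomfort. If the withheld text contains a safety call in the first week, most of the point falls away.

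**A symptom log has its own faults.** Every subject enters with dry eye symptoms and a SPEED score of at least 6 (Section 10.1). Section 12 excludes pre-existing conditions unless they worsen, and the 8.2 endpoint is device-related events. Bare yes/no items counted directly would turn ordinary disease into device harm. This stands, and it shapes the fix.

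**Conclusion.** The point holds in a limited form. On the visible text, nothing solicits safety information between the treatment day and 1 month. Mild procedural events in that interval depend on spontaneous report or on recall about four weeks later and may be under-reported. A transient acuity change may be missed.

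The size cannot be fixed from the documents. Under the assumed 25% incidence with 30% to 70% capture, between 0.9 and 2.1 of 3 expected events would be recorded. For examination-based findings with an assumed mean duration of 7 days, the chance of seeing any case at day 28 is 2% to 6% for incidences of 10% to 30%. Incidence, capture and duration are all assumptions, and the conclusion assumes that the withheld sections contain no solicited contact in the first days.

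The study is descriptive, with no hypothesis or pass/fail criterion (Sections 14.1, 14.3 and 14.4), so no formal decision is at risk. What is at stake is how a low event count and unchanged 1-month acuity may be described. A remedy this cheap is worth making before the first subject is treated.

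**What to change.** 1. In Section 11.5.4, add three daily yes/no items to the Lubricant Drop log for the first 7 days, each worded as 'new or worse than before treatment': eye or eyelid discomfort; blurred vision; eyelid redness or swelling. Record start and resolution dates for each.
2. At the 1-month visit the investigator reviews every positive entry and records it on the Adverse Event Form with severity and relationship, as Section 12 requires.
3. State in Section 8.2 that only entries assessed as device-related count in that endpoint. State in Section 14.4 that all logged entries are also tabulated descriptively.
4. State that the 1-month acuity result does not exclude transient early changes. A log cannot recover acuity that was not measured.

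**Cost.** Three items and their dates on a log that subjects already complete daily, a few sentences of protocol text, and some review time at an existing visit. No extra visit, staff or procedure is needed. More mild transient events are likely to be reported than in the pilot, and some may reflect the underlying dry eye disease. With no control group these cannot be fully separated, and the report should say so.

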4 STUDY OBJECTIVE

The objective of the study is to evaluate the long-term clinical utility, safety, and effectiveness of re-treatment with the TearCare™ System in adult patients with dry eye syndrome who had previously been treated with the TearCare System.

5 BACKGROUND AND JUSTIFICATION FOR THE STUDY

Dry Eye Syndrome is a chronic eye condition that can cause an array of symptoms in patients, ranging from periodic ocular discomfort to severe corneal inflammation, scarring, and vision loss.^{1,2} Approximately 1/3 of patients visiting their eye doctor suffer from dry eye. It is approximated that 23 million people over age 20 suffer from dry eye in the U.S.

Each year in the U.S., billions of dollars are spent on topical lubricants, medications, tear duct occlusions, and other treatments to control the chronic condition. For an individual patient, the annual direct cost ranges from \$678 per year for mild cases to \$1,200 annually for severe cases. Moreover, there is a great cost to society in terms of decreased productivity due to the symptoms of dry eye. Essentially, not only do dry eye patients directly suffer, but there is also a burden to healthcare, employers, and society.

Normal tears coat the ocular surface and perform many functions, including lubrication of the ocular surface, protection from infection, nourishing the ocular surface cells, and providing an optically clear surface to properly refract light. Tears consist of three layers:

1. An underlying mucin layer which acts as a wetting agent to spread tears uniformly on the ocular surface to prevent beading or irregularity;
2. An aqueous layer to maintain an optically clear medium and to keep the ocular surface moist and healthy; and
3. A superficial layer to retard evaporation of the aqueous layer.

When any of these layers is disturbed, tears may lose their protective and optical properties leading to a constellation of symptoms, including those associated with dry eye.

A horizontal line with four black rectangular redaction boxes stacked vertically on it, spanning most of the page width.

A great deal of evidence suggests that obstruction of the meibomian glands, which are the glands on the eyelid that produce the lipid layer of tears, is strongly associated with evaporative dry eye syndrome.^{3,4,5,6} It is estimated that evaporative dry eye syndrome accounts for 65-85% of dry eye cases. As these glands become either inflamed or obstructed, their ability to supply the essential lipids to the ocular surface is diminished. This, in turn, leads to rapid evaporation of tears and thus to evaporative dry eye.⁷ When this occurs, it can result in ocular discomfort and, in many cases, ocular surface disorders that can affect vision.

One of the most commonly prescribed treatments for evaporative dry eye and meibomian gland dysfunction is the use of warm compresses. It is believed that the heat from warm compresses helps melt the oily obstructions in the meibomian glands and helps reduce gland inflammation, thereby helping to restore the ability of the meibomian glands to effectively secrete oil onto the tear film and prevent rapid tear evaporation. It has been shown that warm compress therapy can lead to improved lipid production and flow on to the tear film.^{8,9,10} This improved lipid delivery is associated not only with an improvement in the profile of the tear film but also an improvement in patient symptoms.^{11,12,13} The tear film is demonstrably thicker and more stable with an increased contribution of lipid to its surface.^{14,15,16} However, many

[figure not shown]

factors contribute to poor penetration of warm compress therapy in the dry eye population. More specifically, warm compress therapy has failed to achieve widespread acceptance among patients because:

- It is inconvenient and disruptive to a patient's schedule
- The temperature necessary to achieve an effective AND safe compress is difficult to achieve and maintain at home^{17,18,19}
- Warm compresses, when used at home, tend to cool quickly thereby diminishing their efficacy
- Some patients may over heat the compress putting them at risk for injury^{20,21}
- Patients are not able to enhance the effect by expressing molten secretions from their meibomian glands as a physician routinely does for his/her patients.

Various approaches to heating the eyelids have been proposed, but often they may be too cumbersome or costly for patients.^{22,23,24,25,26}

Sight Sciences has developed a novel device, the TearCare™ System, to deliver controlled, precise heat to the meibomian glands for 12 minutes in the monitored setting of an ophthalmologist or optometrist office. (Refer to Section 6, Description of Device, below.) The TearCare session is then followed by routine manual expression of the meibomian glands by the physician. The goal of this is to more effectively and conveniently treat dry eye with an accepted proven treatment.

This study will enroll subjects who had been previously treated with the TearCare System over one year ago as part of their participation in the TearCare arm of the TearCare pilot study. This extension of the pilot study is being conducted in order to evaluate the long-term safety and effectiveness of re-treatment with the TearCare System.

